- Remedi staff - Staff will be interviewed (most probably as part of a focus group as occurred in the pilot study) at the start of the trial and then again towards the end of the first year. Participants will be those working directly on the project (project managers and all mentors). This is expected to be around 12 individuals.
- Practitioners in referring organisations – covering the 10 local authority areas in Greater Manchester.

- CYP aged 10 to 17 who are participating in the both the treatment and control interventions. We will aim to interview 10-15 individuals. These CYP would be sampled purposively to reflect the different potential groups of CYP and referred into the different aspects of the intervention.
- Parents/Carers of CYP who have received the restorative-based family component (5-10 individuals).
- Victims who have been involved in the RJ component (5-10 individuals).

For the final three groups where only a sample of participants can be interviewed, we will seek a maximum variation sample (Schreier, 2018) to give a range of different backgrounds, experiences, referral routes, aspects of the intervention and ethnic backgrounds. Thank you tokens in the form of shopping vouchers (£20) will be offered to those participating. In order to take part in an interview, participants will need to be able to communicate in English.

Analysis

For the qualitative data, all interviews and focus groups will be audio-recorded and transcribed. Data will be analysed using Braun and Clarke’s (2021) thematic techniques. NVIVO will aid data analysis and interpretation. We recognise that some individuals may be reluctant to be recorded and, in those cases, a written record will be made and these notes will be analysed in the same way. Collection and analysis of qualitative data will be an iterative process, with both occurring in parallel – enabling emerging themes to be investigated in later interviews.

Table 5: IPE Methods overview

Research methods	Data collection methods	Participants/ data sources (type, number)	Data analysis methods	Research questions addressed
Qualitative	Interviews / Focus groups	CYP (N=10-15 per year) Remedi staff (N=12, to be interviewed throughout the intervention to counter staff turnover) Referrers (N=8-10 during the efficacy study) Victims (N=5-10 per year) Families (N=5-10 per year)	Thematic	1. Has the RM intervention been implemented as planned across Greater Manchester? 2. How has the RM intervention been

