	
measure(s) (instrument, scale, source)
	
The first three scores are measured with the Strengths and Difficulties Questionnaire (SDQ). The remaining two scores (4 & 5) are measured with the Self-Reported Delinquency Scale (SRDS).
 
The SDQ and SRDS are completed by CYP at the point of consent, end of the intervention and 6 months after the end of the intervention as a follow-up (for CYP who start the interventions in the first 18 months of the trial).
 
For the SDQ CYP are asked to recall over the past 6 months, a period defined in the measure. For the SRDS, CYP are asked to recall over the past 3 months, this was a period defined for this study, in consultation with Remedi.
 
Scales are 0-20 for the internalizing and externalizing scores and 0-40 for the total difficulties score. Variety of delinquency ranges from 0-19 and volume of delinquency ranges from 0-198 (this excludes the scoring for Question 16, which is different from the other questions).
 
In the pilot study 73% of CYP consented into the interventions completed the initial questionnaires, and between one third and one half completed the end point questionnaires. We would expect these rates to be similar for this efficacy study and so could expect to receive around 257 initial questionnaires and 148 end point questionnaires. Six-month follow up questionnaires were not completed as planned during the pilot study and so we cannot use these completion rates to estimate the expected number of completed questionnaires during the efficacy study. However, we would expect completion rates to be lower than those at the end of the interventions, due to the break in contact with the CYP. As such we estimate between 10-20% of CYP will complete these questionnaires, which would equate to between 35-70 questionnaires. The expected attrition rate will affect the power of the analysis for these secondary outcomes.

Baseline for primary outcome
	
variable
	
The primary outcome of interest is the number of contacts of the CYP with the police, as perpetrators, victims or missing episodes.

	
measure (instrument, scale, source)
	
Police contact data will be taken from Greater Manchester Police administrative records for events 1 year prior to the intervention. Police contact data is a discrete count variable starting at 0.

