### Sample size calculations overview

	Protocol	Randomisation
Minimum Detectable Effect Size (MDES)	0.3	0.3
Alpha	0.05	0.05
Power	0.8	0.8

		Protocol	Randomisation
One-sided or two-sided?		Two-sided	Two-sided
Number of participants	intervention	176	176
	control	176	176
	total	352	352

The planned number of the trial participants is 352 CYP in its one year of implementation, 176 in the RM group and 176 in the RC group. The sample size is such that the trial is sufficiently powered to detect a Cohen’s d of at least 0.3 with probability 80%, which is in line with the funder guidelines and the previous literature.

The “simple” randomisation method will be used, which is a robust method against selection and accidental biases. We will use the statistical software package Matlab to implement the randomisation. Automated randomisation will ensure that the process is transparent and reproducible.

The above rest on the assumption that the alpha is equal to 0.05 and that the power is equal to 0.8. The minimum detectable effect size is equal to 0.3 as measured by Cohen’s d.

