### **Secondary outcome analysis**

In this part of the analysis, the aim is to answer the research question: did the Restorative Mentoring intervention (treatment) reduce difficulties and self-reported behaviour measures according to the SDQ and SRDS questionnaires, when compared to the Restorative Choices intervention (control). Furthermore, do these reductions differ by sex, ethnicity, and referral source.

The secondary outcomes for this analysis will include the CYP's emotional and behavioural difficulties and self-reported delinquency.

Emotional and behavioural difficulties are measured by the following three variables:

- 1) Internalizing score – measured on a scale from 0-20
- 2) Externalizing score – measured on a scale from 0-20
- 3) Total difficulties score – measured on a scale from 0-40

Self-reported delinquency is measured by:

4) Variety of delinquency - measured as the sum of the overall categories of delinquency  
Range: 0-19.

5) Volume of delinquency - measured as the sum of magnitudes of delinquency, over all  
categories Range: 0-198.

These variables will be compared across the treatment and control groups to test the null hypothesis of equal means against the two-sided alternative.

The regression analysis takes the form

$$Y_i = \alpha + \beta T_i + Z_i' \gamma + u_i \quad (2)$$

where  $Y_i$  is the secondary outcome for individual  $i$  (one of the aforementioned SDQ and SRDS variables).  $T_i$  is an indicator variable equal to 1 if  $i$  was assigned to treatment and 0 if  $i$  was assigned to the control group.  $Z_i$  is a vector of individual characteristics that are not affected by the intervention (sex, age, ethnicity, district, prior contact with the police, and referral source).  $u_i$  represents the random errors, which are not observed. Given that  $Y_i$  is a continuous variable we will employ a linear regression. The key assumptions that we will use is that the observations are independent to each other, there is mean independence  $E(u_i|T_i, Z_i) = 0$ , and that not all CYP have identical  $T_i$  and  $Z_i$  (no perfect multicollinearity). These assumptions are weak and easily satisfied.

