### **Subgroup analyses**

Given the potential for treatment to have different effects on individuals or specific groups, tests for heterogenous treatment effects will be performed to analyse whether individuals respond differently to treatment based on three observable characteristics: sex, ethnicity, and referral source. In this case, we will estimate the regressions specified above for subsamples based on these characteristics (male, female, white, non-white, police, youth services). Although the individual randomisation process was not stratified based on these

---

 The subgroup analysis will not be done in interactions of subgroups due to sample size limitations.

groups, if the sample size is sufficiently large to do a powered analysis, reporting results for groups defined post-randomisation could provide supplementary insights alongside the primary findings (Duflo et al. 2007). Therefore, this part of the analysis will also be exploratory, and we acknowledge potential limitations in terms of statistical power, since the sample size for each subgroup will be small.

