### **Longitudinal follow-up analyses**

One follow up point for measurement is specified – 6 months after the end of the intervention for the secondary outcomes. This will enable the estimation of potential longer lasting effects of the intervention by performing the same statistical analysis described above with data covering a longer period of time.

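### The six-month SDQ/SRDS analysis reuses the full covariate model, probably with nine district indicators, on an expected 35-70 forms; if the covariates are not prognostic, adjustment costs up to 21-43% of the information

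*SAP*

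**What the plan says.** The SAP section Longitudinal follow-up analyses sets one later time point for the questionnaires, six months after the intervention ends, to be analysed by "performing the same statistical analysis described above with data covering a longer period of time". The protocol, under Longitudinal follow-ups, likewise says that the later analysis mirrors the main one.

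The analysis being reused is in the SAP section Secondary outcome analysis and has two parts. The first compares the arms "to test the null hypothesis of equal means against the two-sided alternative". The second is equation (2), a linear regression on arm and "sex, age, ethnicity, district, prior contact with the police, and referral source". The baseline SDQ or SRDS score is not in that list, although the SAP Design overview shows that it is collected. The coding of district and ethnicity is not given.

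The Design overview puts six-month completion at 10-20%, "which would equate to between 35-70 questionnaires". The protocol's process evaluation describes referring practitioners as "covering the 10 local authority areas in Greater Manchester". Under Subgroup analyses the SAP adds that "we will estimate the regressions specified above for subsamples based on these characteristics", subject to sample size.

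**The concern.** A model chosen for a larger sample is carried unchanged to the smallest dataset in the trial. With few forms per coefficient, chance correlation between arm and the covariates inflates the variance of the arm effect. Covariates repay that cost only by explaining outcome variance. Nine indicators for districts holding about 3-7 forms each are the least likely to do so, and they are most of the model.

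At stake is precision in the only analysis of longer-term effect on the secondary outcomes. Two estimates of possibly quite different precision would be reported at six months with no stated priority between them.

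**Working it through.** **Reproducing the plan's figures.** "The planned number of the trial participants is 352 CYP" (176 per arm), where "the alpha is equal to 0.05 and that the power is equal to 0.8". A two-sided t-test for d = 0.3 gives 176 per arm, so 352 reproduces. 10% and 20% of 352 are 35.2 and 70.4, so 35-70 reproduces.

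**Counting coefficients.** Assumed coding: ten districts give nine indicators; sex, ethnicity and referral source are binary, as in the SAP's subgroup definitions; age and prior contact are linear.

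Intercept 1 + arm 1 + sex 1 + age 1 + ethnicity 1 + district 9 + prior contact 1 + referral source 1 = 16. Adjustment adds q = 14 terms.

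- n = 35: 35/16 = 2.2 forms per coefficient, 19 residual degrees of freedom.
- n = 70: 70/16 = 4.4 forms per coefficient, 54 residual degrees of freedom.

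**Cost when the covariates explain nothing.** Expected variance inflation of the arm effect is about (n − 3)/(n − 3 − q), and the information lost is 1 − 1/inflation = q/(n − 3). The simulation used ten equal-sized districts and independent covariates.

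| n | Inflation, formula | Inflation, simulated | Loss, formula | Loss, simulated |
|---|---|---|---|---|
| 70 | 67/53 = 1.26 | 1.26 | 14/67 = 20.9% | 20.9% |
| 35 | 32/18 = 1.78 | 1.75 | 14/32 = 43.8% | 42.8% |

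At the 148 end-point forms the simulated inflation is only 1.11, so the problem is mainly one of the six-month analysis.

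**Net cost when the covariates explain a share R² of outcome variance.** Relative information = (1/inflation)/(1 − R²). The documents give no R², so a range is shown.

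| R² | Net change, n = 35 | Net change, n = 70 |
|---|---|---|
| 0 | −43% | −21% |
| 0.1 | −36% | −12% |
| 0.2 | −28% | −1% |
| 0.3 | −18% | +13% |
| 0.4 | −5% | +32% |
| 0.5 | +15% | +58% |

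Break-even is at R² of about 0.43 (n = 35) and 0.21 (n = 70).

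**District's share.** Without district q = 5, and the formula gives 67/62 = 1.08 and 32/27 = 1.19. For district to pay for itself it must explain 1 − 1.08/1.26 = 14% (n = 70) or 1 − 1.19/1.75 = 32% (n = 35) of the variance left by the other covariates.

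**Power for d = 0.3, unadjusted against worst-case adjusted.** 23% against 19% at n = 70; 14% against 9% at n = 35. The effect detectable with 80% power is 0.68 against 0.77 and 0.98 against 1.32.

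**Subsamples.** Assume a subgroup with 30% of the forms: 0.3 × 35 ≈ 10 and 0.3 × 70 = 21. At 10 forms the model with district almost never yields an arm effect (inestimable in at least 97% of simulated sets). At 21 forms, with indicators for empty districts dropped, it almost always fits, but the median variance inflation is about 2.5, so the standard error rises by √2.5 − 1 ≈ 58%.

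**The case against.** A reader might infer that adjustment will discard 21-43% of the six-month data and that the adjusted estimate must be the less precise one. The documents do not support that. The figures assume that all the covariates together explain none of the outcome variance. Age, sex and prior police contact may well be prognostic, and at 70 forms an R² of 0.2 all but removes the loss. The coefficient count also rests on assumed coding, and the ten areas come from a description of where practitioners are interviewed, not from the SAP.

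Nor is the adjusted model the only six-month estimate. The protocol's Analysis section promises simple differences in means for every outcome, and the SAP's secondary analysis begins with such a comparison; both carry over to six months at no adjustment cost. The SAP also calls the secondary analysis exploratory and admits limited power, and the form count limits this analysis far more than the covariates do.

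A reader might further infer that the planned six-month subgroup regressions cannot be run. That holds at about 10 forms, but not at 21, where the fit is poor rather than impossible. The subgroup sizes are assumed, and the SAP already makes subgroup reporting conditional on sample size, though without a threshold.

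All of this limits the size of the point. What it leaves standing is the case on district: no reason is given to expect districts this thinly filled to explain 14-32% of the remaining variance. The caveats on power concern the number of forms, not a model that may make the shortage worse. For the primary outcome the SAP names the unadjusted ITT estimate as the headline; for the secondary outcomes it names none.

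**Conclusion.** The point holds as an avoidable and conditional loss of precision in an exploratory analysis. Under categorical district and binary ethnicity, the reused model costs up to the equivalent of 21% of the forms at n = 70 (about 55 of 70 remain) and 43% at n = 35 (about 20 of 35). The net loss falls to zero if the covariates explain about 21% or 43% of outcome variance, so a net loss is more likely at the lower end of the expected form count. District carries most of the cost. More ethnicity categories would raise the coefficient count; districts with no six-month forms would lower it slightly. No data are lost to the trial, since the unadjusted comparison remains. The gaps to close are the unreduced model and the unstated priority between the two estimates.

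**What to change.** In the SAP section Longitudinal follow-up analyses, replace the reuse of the full analysis with a named six-month model that omits district and referral source: for example arm, the baseline score of the same SDQ or SRDS outcome, age and sex. The covariates should be named now, so that no choice is left until the data are seen. With three covariates the worst-case inflation by the formula above is 67/64 = 1.05 at n = 70 and 32/29 = 1.10 at n = 35.

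State also that the unadjusted comparison is reported alongside, say which of the two leads, and omit district from any subsample regression on six-month questionnaire outcomes.

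The cost is a few sentences in the SAP. The analysis gives up adjustment for district and referral source. The baseline score will be missing for some participants (the plan expects about 257 of 352 initial questionnaires), so the text should say how those cases are handled.

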### **Imbalance at baseline**

Balance tests will be performed to formally test the random assignment of CYP to treatment and control groups. We will perform t-tests to evaluate whether there is significant differences in mean characteristics between treatment and control groups. The baseline characteristics we will test are: sex, age, ethnicity, district, the number of contacts with the police in the year prior to referral, and referral source.

### **Missing data**

The primary outcome analysis will be performed according to the ITT principle (described above). The primary outcome is measured by police administrative data and therefore outcome variables for CYP that have disengaged with the intervention will still be collected, reducing concerns of missing values for the primary outcome variable. For the control variables that might be missing, we will follow YEF guidelines and in a first step we will attempt to establish the mechanism behind missingness using a logistic regression model. Depending on the pattern of missing data, either multiple imputation or sensitivity analyses will be conducted.

### **Compliance**

The evaluation has been designed to engage CYP in both treatment and control groups. Implementation of the intervention will be monitored to make sure that compliance is near

perfect by introducing a fidelity check agreement. However, it is expected that some CYP might disengage, justifying the ITT and LATE analysis proposed in the analysis section above.

The ITT approach analyses CYP based on their original group assignments, irrespective of whether they completed the treatment or not. The LATE approach estimates the effect of the treatment exclusively for CYP who comply with their assigned treatment, defined as (J-PAL, 2023):

$$LATE = \frac{E(Y_i|z_i = 1) - E(Y_i|z_i = 0)}{E(d_i|z_i = 1) - E(d_i|z_i = 0)} \quad (3)$$

Where  $Y$  is the outcome for CYP  $i$  (as specified above);  $z$  represents the treatment assignment, with a value of 1 if the CYP was assigned to treatment (RM) and 0 otherwise;  $d$  represents whether the treatment was received, equal to 1 if the CYP engaged with treatment and 0 otherwise. In this equation, random treatment assignment serves as an instrumental variable for the status of treatment. As we have available data on the number of sessions received by each CYP we will define  $d_i = 1$  if the CYP completes the full intervention.

The LATE estimation relies on a few assumptions. The first is the independence assumption that is automatically satisfied because of random assignment of the treatment. The estimation also requires a positive fraction of compliers and that the monotonicity (being assigned to treatment does not reduce the likelihood of being treated) and exclusion restriction assumptions (CYP respond to the treatment directly, rather than just to their assignment to receive it, therefore treatment assignment does not change the outcome) hold (J-PAL, 2023). In addition, we assume that compliance does not vary with treatment assignment. The experimental design, which ensures perfect blindness, guarantees that this assumption holds true. In other words, CYP who consent to participate in the intervention do not know whether they are going to receive RM or RC (Gerber, Green, Kaplan and Kern, 2010; EGAP).

### **Presentation of outcomes**

The effect size will be reported based on the Incidence Rate Ratio or Cohen's  $d$  formulas. The incidence rate ratio (IRR) is given by:

---

 This means that the CYP is classified by REMEDI as a closed case, which indicates that the CYP has completed all the sessions (occasionally 1 or 2 sessions under or over the specified amount). While there is no agreed definition of compliance, we follow this strict definition after discussion with the intervention provider.

$$\text{IRR} = \exp(\hat{\beta}),$$

where  $\hat{\beta}$  is the maximum likelihood estimate from the Poisson and Negative Binomial distributions. The confidence interval is estimated by applying the delta method to the inverse of the estimated Fisher Information matrix.

Cohen's d is equal to the difference in the average of the variable in the treatment and control group divided by the standard deviation of the pooled sample:

Cohen's

$$d = \frac{\bar{Y}_t - \bar{Y}_c}{\text{s.e.}(Y)}$$

The confidence interval for d is given by

$$[d - 1.96 \times \sigma(d), d + 1.96 \times \sigma(d)]$$

where

$$\sigma(d) = \sqrt{\frac{N_1 + N_2}{N_1 N_2} + \frac{d^2}{2(N_1 + N_2)}}.$$

The t-tests and confidence interval formulas are based on the normal distribution as the sample size is expected to be large. These will be used to examine the statistical significance of the estimated coefficients. The formula for t-statistic is given by

$$t = \frac{\hat{\beta}}{\text{s.e.}(\hat{\beta})}.$$

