### Primary outcome analysis

The aim of the analysis is to answer the research question: did the Restorative Mentoring intervention (treatment) reduce post-treatment contact with the police compared to the Restorative Choices intervention (control)?

The primary outcome for this study is contact with the police, defined as the number of times the CYP appear in the police data as perpetrators, victims or for missing person episodes. These data will be taken from Greater Manchester Police administrative records.

Contact with the police is a discrete count variable starting at 0. These data will be collected one month before the trial ends, for a period 1 year prior to the recruitment date and for 3 months after completion of the intervention for all CYP.

It should be noted that the primary outcome, which is police contact with the CYP, is susceptible to biases in reporting and recording of crimes. These biases may stem from a number of factors, including characteristics of both the victim and the offender, such as ethnicity and gender. Nevertheless, we anticipate that the RCT design remains robust to these biases, as randomisation into the treatment and control groups is conducted independently of the police's reporting and recording of crimes.

There are two ways of analysing the data, depending on the distribution assumed for the dependent variable, which is total police contacts. As a discrete count random variable, it may be assumed to follow a Poisson or Negative Binomial distribution. However, if the mean of that distribution is far from 0, the Poisson and Negative Binomial distributions may be approximated by the continuous normal distribution. It is not clear a priori which distribution will be the better approximation, and therefore we consider below both scenarios. In any case, we do not expect major differences; the issue of whether a variable should be treated as continuous or discrete has received much attention in the randomized control trial literature and the main finding is that unless the outcome is binary or it is a "time to a first event", information will not be lost when treating a count variable as a continuous one, see, e.g. Herbison et al. (2015).

For the analysis, the headline estimate will be derived from an intention to treat effect (ITT), denoted by  $\beta$  in the regression:

$$g[E(Y_i|T_i)] = \alpha + \beta T_i,$$

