where  $Y_i$  is the primary outcome for individual  $i$ , and  $T_i$  is an indicator variable equal to 1 if person  $i$  was assigned to treatment and 0 if person  $i$  was assigned to the control group. The function  $g$  is the link function and is equal to the natural logarithm function if the dependent variable is assumed to be Poisson or Negative Binomial.

Hypothesis testing in the above regression complies with the power predictions of the study. The effect size will be measured by the Incidence Rate Ratio if the data are assumed to be Poisson or Negative Binomial, and by Cohen's  $d$  if they are assumed approximately normal. If the data are Poisson/Negative Binomially distributed, the necessary sample size to detect a "small" effect of at least 1.22, see e.g. Cohen (1992) and Olivier et al. (2017), with  $\alpha=0.05$  and

80% power is 322 CYP equally split between the treatment and control groups. Alternatively, if the data are assumed to be normally distributed, then to detect a “small” effect size of at least 0.3 is 352 CYP. Therefore, a sample of 352 CYP will lead to as sufficiently powered study irrespective of the data distributional assumption.

We will additionally estimate a regression with covariates:

$$g[E(Y_i|T_i, Z_i)] = \alpha + \beta T_i + Z_i' \gamma,$$

where  $Z_i$  is a vector of individual characteristics that are not affected by the intervention (sex, age, ethnicity, district, the number of contacts with the police in the year prior to referral, and referral source). The analysis below depends on the over-arching assumption that the sample of observations are independent to each other. This is reasonable as the sample is only a small subset of the whole population.

The dependent variable here is a count variable and it is highly likely that the lower values will have much higher frequency, in other words it is heavily skewed to the right. This feature of the data suggests that they are best analysed using Poisson regression. Mathematically, the Poisson regression takes the form:

$$Y_i | \lambda_i \sim Poi(\lambda_i)$$

where  $\lambda_i = \alpha + \beta T_i + Z_i' \gamma$ .

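### The SAP leaves the headline model for police contacts open (normal with Cohen's d, or count with IRR), and its IRR interval can disagree with its own test

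*SAP*

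**What the plan says.** **Choice of model.** In the SAP, Primary outcome analysis, the police-contact count may be treated as Poisson or Negative Binomial, or as approximately normal if its mean lies well away from zero. The SAP adds: "It is not clear a priori which distribution will be the better approximation, and therefore we consider below both scenarios". Presentation of outcomes then allows the effect size to be either an IRR or Cohen's d.

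**What is fixed.** The headline estimate is the unadjusted ITT coefficient beta. The text leans towards Poisson because the count is expected to be strongly right-skewed, and it moves to Negative Binomial if the variance exceeds the mean. The link is stated in words to be the natural logarithm for either count model.

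**Interval and test.** Presentation of outcomes defines the IRR as exp(beta-hat) and says of its interval: "The confidence interval is estimated by applying the delta method to the inverse of the estimated Fisher Information matrix". The same section tests beta by the ratio of its estimate to its standard error, using the normal distribution.

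**Notation.** After "Mathematically, the Poisson regression takes the form", the SAP sets the Poisson rate lambda_i equal to the bare linear predictor, covariates included. Cohen's d is described as a mean difference "divided by the standard deviation of the pooled sample", but the printed denominator is s.e.(Y).

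**Protocol.** The Analysis section repeats the Poisson-then-Negative-Binomial sequence. Table 4 lists Poisson, Negative Binomial, t-test and Cohen's d for the police data without ranking them.

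**The concern.** A SAP should settle, before outcomes are seen, which model, effect measure, interval and p-value carry the primary conclusion. Here three choices remain: normal or count, Poisson or Negative Binomial, and how the IRR limits are built.

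The normal route is a live option. SAP footnote 2 gives a pilot control mean of 1.8 and expects a much higher one in this trial, and no value is given at which the mean becomes large enough. The Poisson/Negative Binomial choice matters most for error control, because model-based Poisson standard errors are too small when counts are overdispersed.

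The interval raises a separate matter. Limits for beta come directly from the inverse Fisher information; the delta method is needed only to move to exp(beta). The natural reading is therefore IRR x (1 ± 1.96 SE), which is symmetric about the IRR. The planned test is symmetric about beta on the log scale. The two can disagree on whether the result is significant, and no rule says which prevails.

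**Working it through.** **Inputs.** Two-sided alpha 0.05 and power 0.8 ("The above rest on the assumption that the alpha is equal to 0.05 and that the power is equal to 0.8"); target effect d = 0.3; total sample size 352 ("The planned number of the trial participants is 352 CYP"), or 176 per arm (all SAP, Sample size calculations overview). Control mean 1.8 (SAP footnote 2, pilot). The dispersion k, with variance = mean + k x mean², is not in the documents; it is assumed and varied from 0 (Poisson) to 2.

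**1. The plan's own figure.** n per arm = 2(z₀.₉₇₅ + z₀.₈)²/d² = 2 x 7.849/0.09 = 174.4, so 175 per arm. The t-based version gives 175.4, so 176 per arm. The total of 352 reproduces for the normal route.

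**2. Cost of keeping Poisson when counts are overdispersed.** Under the null, variance/mean = 1 + 1.8k. The true standard error exceeds the Poisson one by the square root of this ratio, so two-sided error ≈ 2Φ(−1.96/√(1 + 1.8k)).

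| Assumed k | Variance/mean | Square root | Null error |
|---|---|---|---|
| 0.5 | 1.9 | 1.378 | 0.155 |
| 1 | 2.8 | 1.673 | 0.241 |
| 2 | 4.6 | 2.145 | 0.361 |

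**3. Tails of an interval built on the IRR scale.** With means m0 and m1, SE = √((1/m0 + 1/m1 + 2k)/176). Under the null this is 0.0795 (k = 0), 0.133 (k = 1) and 0.170 (k = 2). The interval excludes 1 in favour of RM with probability Φ(−ln(1 + 1.96 SE)/SE), and against RM with probability Φ(ln(1 − 1.96 SE)/SE).

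| Assumed k | In favour of RM | Against RM | Total |
|---|---|---|---|
| 0 | 3.4% | 1.7% | 5.1% |
| 1 | 4.1% | 1.2% | 5.2% |
| 2 | 4.5% | 0.9% | 5.4% |

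Totals are taken before rounding. Balanced tails would be 2.5% each.

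**4. A case where interval and test part.** k = 1, observed IRR 0.78:
- SE = √((1/1.8 + 1/1.404 + 2)/176) = 0.136.
- IRR-scale limits: 0.78(1 ± 1.96 x 0.136) = 0.57 to 0.99, excluding 1.
- Test of beta: ln 0.78/0.136 = −1.82, p = 0.068.
- Exponentiated limits: exp(ln 0.78 ± 0.267) = 0.60 to 1.02, agreeing with the test.

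Below 1, the two disagree only for an observed IRR of about 0.765 to 0.789 when k = 1, or 0.850 to 0.861 under Poisson.

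**5. How often.** Simulation of 200,000 trials per setting, with dispersion treated as known, gave coverage of 0.945 to 0.950 for the IRR-scale interval and 0.949 to 0.951 for the log-scale one. At a true IRR of 0.82, the two disagreed about excluding 1 in 5% (k = 0), 8% (k = 1) and 9% (k = 2) of trials. The IRR-scale interval excluded 1 more often: 71% against 66%, 39% against 31%, and 30% against 21%.

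**The case against.** **There is a rule of sorts.** The SAP leans to Poisson, states when to leave it, and fixes the unadjusted ITT contrast. A reader might infer that the analyst has a free hand; that goes too far. What is missing is a test or cut-off for the switch and any operational criterion for the normal route. Nor is the 24% a forecast. With variance 1.9 to 4.6 times the mean, an analyst who checks should see the overdispersion and switch. The figure is the price of not switching.

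**The choice may matter little.** The SAP expects no major differences between the count and continuous treatments. As far as the test goes, this has force: in simulation, unadjusted Negative Binomial and linear tests disagreed in only about 1% of trials. The reported effect measure still remains undetermined. The SAP's statement that 352 is enough under either distribution concerns power, not which result is the headline.

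**The delta method is legitimate.** This stands. The SAP neither prints the limits nor calls them symmetric; the IRR-scale reading is an inference from its wording. A reader who sees only the 4.1% tail might infer inflated error, but the opposite tail falls to 1.2% and the total stays near 5%. The example in step 4 lies inside a narrow window and rests on an assumed dispersion.

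**The formulas can be read as intended.** A reader might infer an identity-link Poisson model, in which a fall from 1.8 to 1.48 (difference −0.32) would be reported as exp(−0.32) ≈ 0.73 and not 0.82. Or a reader might infer a Cohen's d inflated by √352 = 18.8. The documents support neither. The log link is stated in the same section, the IRR is exp(beta-hat), and the faulty line belongs to the additional covariate model, not the headline. The d formula is contradicted by its own sentence, and the printed sigma(d) is the usual one for a d scaled by the standard deviation.

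**Conclusion.** The point holds on two counts.

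First, the SAP does not determine one headline model and effect measure before outcomes are seen. The normal-or-count choice has no usable criterion, and the Poisson-to-Negative-Binomial switch has no named test. Failing to switch would be costly: two-sided null error of about 24% at dispersion 1, and about 15% to 36% across 0.5 to 2.

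Second, the IRR interval, on the natural reading of its description, is valid overall but lopsided towards declaring benefit (3.4% to 4.5% in favour of RM, 1.7% to 0.9% against) and can contradict the planned test of beta.

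These sizes rest on 176 per arm, the pilot mean of 1.8 and assumed dispersions. The second also rests on limits built on the IRR scale. The lambda_i line and s.e.(Y) are notation slips and do not show that a wrong analysis is planned.

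**What to change.** Before outcomes are seen, amend the SAP to:

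1. Name one headline analysis: the unadjusted ITT Negative Binomial regression with log link, effect reported as the IRR. Robust standard errors are one acceptable safeguard. No data-driven switch from Poisson is then needed.
2. Make the linear model with Cohen's d a sensitivity analysis.
3. Give the IRR interval as exp(beta-hat ± 1.96 SE), so that it always agrees with the test of beta.
4. Correct the notation: log(lambda_i) = alpha + beta T_i + Z_i'gamma in Primary outcome analysis, and the standard deviation in place of s.e.(Y) in Presentation of outcomes.
5. Align the protocol's Analysis section and Table 4 with these choices.

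The cost is wording only, with no extra data. The reported IRR limits move up slightly: at dispersion 1 and an observed IRR of 0.82, from 0.602–1.037 to 0.628–1.069.
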